For Community Place and Alpert Jewish Family and Children's Service (AJFCS), we are matching participants on the following characteristics: age group (<70, 70-80, and ≥ 80 years), gender (male and female), race/ethnicity (African American, Hispanic, and non-Hispanic White) and at Community Place we are also matching based on County (Monroe or Livingston).

At both all sites we are going to recruit people from the waiting list and match them with people already receiving peer to peer services. Every month research staff at UW will ask to see the matching spreadsheet as a way to monitor how matching is progressing at each site.

Enrolling more than one person per household (added 1/14/2016)

As of February 22, 2016, we will only enroll one person per household. This is the protocol for determining which person from the household we will enroll.

- a. If Participant A is enrolled in the study (signed the consent form) and they say they would like their partner would like to participate, the research staff person will let them know that according to study protocol we are only allowed to enroll one person per household. Participant A will be the person that is enrolled in the study.
- b. If prior to enrollment a study staff person is informed that both partners in a couple want to participate in the study. The staff person will let the two participants know that we can only enroll one participant from the couple. If we only need one person then the research staff will screen and enroll that person.
- c. If we know in advance there is a couple interested in participating and both people are needed for the study then we will randomly select one person per household. In this case you should screen both participants. If both participants are deemed eligible to participate you should first assign one participant heads and one participant tails. Then you should pull out the randomization envelope and open it. This envelope will tell you which participant you will enroll. At this time you will discard the envelope.

Enrollment in Study

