The primary analyses for comparative effectiveness will be based on two-sample independent tests such as t-test, Wilcoxon rank sum test, Fisher's exact test or chi-square test of the outcome measures. The choice of analytic method will depend on whether the outcome measures are continuous or categorical. These tests will be performed at a two-tailed significance level of 0.05 without adjustment for multiplicity. Health care utilization and nursing home placement rates and self-rated health, wellness, depression, and anxiety between the two groups will be compared using a two-sample test again at a two-tailed significance level 0.05.

Subsequent to the primary analyses, regression analyses will be performed for the same outcome measures adjusting for stratification factors and other potential confounders that might influence the outcomes, including an indicator for site. Linear or generalized linear models such as logistic and Poisson regression models will be used depending on the outcome measures. As the intermediary measures of health and overall wellness such as self-rated health, depression, and anxiety in Aim 2 may serve as important mediators of the effect of the peer-to-peer support intervention on the primary outcomes measures in Aim 1, we will use exploratory mixed-effects regression techniques and structural equation models to test and quantify whether and to what extent the effect of the intervention is mediated by intermediary measures of health and overall wellness. We expect missing data due to random drop-out of participants before month 12 and to a lesser extent loss due to death of participants before month 12. Missing data will be handled as per the recent National Research Council report on the topic.⁷⁷ Death before month 12 will be considered a competing event, and will be handled using the appropriate method.⁷⁸

Given the diverse nature of our sample, we plan to carry out the statistical analyses for Aims 1 and 2 for a limited number of subgroups. We will conduct subgroup analyses based on race/ethnicity (African American, Hispanic and non-Hispanic White), gender (male vs. female), age group (< 70, 70-80 and ≥ 80 years), and language (English- vs. Spanish-speaking) and by the three sites. These subgroup analyses will be conducted to evaluate the internal consistency of intervention effect, and subgroup by intervention interaction tests will be used to assess the internal consistency.

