Randomization and matching In order to reduce potential bias further, participants from the AJFCS of Palm Beach will be allocated either to peer-to-peer support (Intervention) or standard community support (Control) in a 1:1 ratio using permuted block randomization, stratified by age, gender and race/ethnicity. Barring randomization in JFS of LA and Community Place of Greater Rochester, older adults already participating in peer-to-peer support and those on the waiting list will be matched on age, gender and race/ethnicity to mitigate potential differences between the two groups. In order to avoid reporting/ascertainment bias, calls will be made to all participating older adults and support staff at 3 and 9 months as outlined in Figure 4 above.

Sample Size Justification Given the total sample size of 720 at-risk older adults, the study has 0.80/0.85/0.90 power to detect the effect size of 0.209/0.223/0.242 for the primary outcome measure of the annualized rate of hospitalization, ED use and institutionalization at a two-tailed significance level 0.05. The effect size here is defined as the difference in the mean annualized rate of hospitalization, ED use and institutionalization between the two groups divided by the standard deviation of the annualized rate assumed to be common in the two groups. Due to random drop-out or loss to competing event of death, the study will have less power to detect the stated effect sizes or will have the stated power for larger effect sizes.

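### The arms are to be balanced by demographic cell within site, but the primary tests ignore this; making the already planned adjusted analysis primary is a cheap, modest improvement

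*SAP*

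**What the plan says.** **Primary analysis.** The SAP (Analysis Plan) states: "The primary analyses for comparative effectiveness will be based on two-sample independent tests such as t-test, Wilcoxon rank sum test", with Fisher's exact and chi-square tests also named. It adds: "These tests will be performed at a two-tailed significance level of 0.05 without adjustment for multiplicity". Regressions of the same outcomes on stratification factors, other confounders and a site indicator are planned, but only after these tests.

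**Design.** The SAP (Randomization and matching) allocates Alpert Jewish Family and Children's Service (AJFCS) participants "in a 1:1 ratio using permuted block randomization, stratified by age, gender and race/ethnicity". At the other two sites, "older adults already participating in peer-to-peer support and those on the waiting list will be matched on age, gender and race/ethnicity". The Protocol (Matching) says of the sites that "we are going to recruit people from the waiting list and match them with people already receiving peer to peer services", and adds county at Community Place. The recruitment goals are equal by arm at every site: 113 + 113 at Community Place, 150 + 150 at AJFCS and 30 + 30 at Jewish Family Service of Los Angeles (JFS of LA).

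**Sample size.** The SAP (Sample Size Justification) states: "Given the total sample size of 720 at-risk older adults, the study has 0.80/0.85/0.90 power to detect the effect size of 0.209/0.223/0.242". The effect size is the difference in mean annualized rate "divided by the standard deviation of the annualized rate assumed to be common in the two groups", that is, the total standard deviation with nothing removed for cells or site.

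**The concern.** When two arms have the same mix of cells, variation between cells drops out of the difference in means. An independent two-sample test still counts that variation in its standard error. If the cells are prognostic, the interval is then wider than it need be, the test runs below its nominal 0.05 level, and some power is lost.

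This is a matter of variance. It would arise with perfectly comparable groups, so it is separate from confounding by health status.

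The opening of the SAP's Statistical Considerations also promises to show how site differences will be controlled in the analyses, and the primary tests do not do so. The same tests serve the utilization rate, nursing home placement and the self-rated measures, so the point applies to all of them.

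**Working it through.** **Inputs from the documents.** Two-sided alpha is 0.05. N is 720, or 360 per arm. The effect sizes d are 0.209, 0.223 and 0.242 (SAP). The protocol's site goals sum to 226 + 300 + 60 = 586, or 293 per arm.

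**Assumed input.** R² is the share of outcome variance explained by site and matching cells. No document gives it, so a range of 0.01 to 0.20 is shown.

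**Step 1: reproduce the SAP.** Power = Φ(d·√(n/2) − 1.96). With n = 360 this gives 0.801, 0.849 and 0.901 at the three effect sizes, which agrees with the stated 0.80/0.85/0.90. The stated power therefore belongs to the independent test and claims no gain from matching.

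**Step 2: effect of balanced cells.** With the standard deviation set to 1 and arms exactly balanced within cells, the true variance of the difference is 2(1 − R²)/n. The independent test uses 2/n. It follows that:

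- SE ratio (independent/adjusted) = 1/√(1 − R²)
- true alpha of the independent test = 2·[1 − Φ(1.96/√(1 − R²))]
- power of the independent test = Φ((d·√(n/2) − 1.96)/√(1 − R²))
- power of the adjusted test = Φ(d·√(n/2)/√(1 − R²) − 1.96)

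With d = 0.209, d·√(n/2) is 0.209 × √180 = 2.804 at 360 per arm and 0.209 × √146.5 = 2.530 at 293 per arm. For example, at R² = 0.10 and 360 per arm, √0.90 = 0.949. The independent test has power Φ(0.844/0.949) = 0.813 and the adjusted test Φ(2.804/0.949 − 1.96) = 0.840.

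| R² | SE ratio | True alpha | Power at 360 per arm, independent vs adjusted | Power at 293 per arm, independent vs adjusted |
|---|---|---|---|---|
| 0.01 | 1.005 | 0.049 | 0.802 vs 0.805 | 0.717 vs 0.720 |
| 0.05 | 1.026 | 0.044 | 0.807 vs 0.820 | 0.721 vs 0.737 |
| 0.10 | 1.054 | 0.039 | 0.813 vs 0.840 | 0.726 vs 0.760 |
| 0.20 | 1.118 | 0.028 | 0.827 vs 0.880 | 0.738 vs 0.807 |

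**Step 3: check of the conditions by simulation.** The simulation used 586 participants, 40 assumed cells and 4,000 runs per setting. The ratio below is the mean independent-test SE over the actual standard deviation of the estimate.

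- Balanced cells: ratio 1.03, 1.07 and 1.12 at R² of 0.05, 0.10 and 0.20, with null rejection of 0.046, 0.037 and 0.027. The adjusted test rejected at 0.048 to 0.050.
- Cells not balanced between arms: ratio 1.01 and 1.00 at R² of 0.05 and 0.10, so the standard error is not too large. At R² = 0.05, adjusting for all 40 cells gave a slightly larger spread (0.0833 vs 0.0819), which argues for main effects over fully crossed cells.
- Balanced cells, but 20% of participants in same-arm household pairs (assumed intraclass correlation 0.3, R² 0.02): ratio 0.97, with rejection of 0.056 unadjusted and 0.059 adjusted. Here the standard error is too small, and adjusting for cells alone does not correct it.

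**The case against.** Several points on the other side stand.

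- **The adjusted model is already planned.** A reader might infer that the precision from matching is thrown away. It is not: the SAP's later regressions adjust for stratification factors and site. The open question is which analysis is primary.
- **The direction is conditional.** A reader might infer that the primary standard errors are definitely too large. That needs prognostic cells, achieved balance and no offsetting clustering, and the documents establish none of these. AJFCS recruits to bucket counts, matching progress is only reviewed monthly, and the Protocol (Unexpected Circumstances) anticipates more refusals among controls. The limit of one person per household began on 22 February 2016, so earlier pairs could push the standard error the other way.
- **The mechanism at AJFCS is unclear.** The SAP randomises there. The Protocol's Matching section lists AJFCS as a matched site, and its AJFCS recruitment section draws controls from the community. These sections need reconciling as a separate matter. Both routes aim at balance by cell within site.
- **The stated power is not broken.** The sample size was calculated for the independent test. At N = 720 that test's power stays at or above 0.80 and rises with R², and its error stays below 0.05. The trial forgoes a gain that it never claimed.
- **Matching was meant to reduce bias.** The SAP gives mitigation of group differences, not precision, as its purpose.

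What survives is that the adjusted analysis is the better primary whether or not matching succeeds. With balanced cells it gives the right standard error. With unbalanced cells it removes measured imbalance that an unadjusted test would leave in the estimate, which matters most at the non-randomised sites.

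**Conclusion.** The mismatch between design and primary analysis is real, small and conservative. If the cells are prognostic and balance is achieved, the independent-test standard error is 0.5% to 12% too large over R² of 0.01 to 0.20. At R² up to 0.10, a reasonable working range for three age bands, gender, race/ethnicity and site, the power gain is 0.3 to 2.7 points at 360 per arm and 0.3 to 3.4 points at 293 per arm: about 0 to 3 points.

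A reader might take a much larger R², such as 0.50, and conclude that power is seriously impaired. Nothing in the documents supports such a value. The shortfall from 720 to 586 costs more, about 8.5 points at d = 0.209 (0.801 to 0.716), but that is a different issue.

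The results rest on the assumed R², exact balance within cells, a normal approximation and no household clustering. This is a cheap improvement of minor severity, not a definite error.

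**What to change.** In the SAP's Analysis Plan, change which analysis is primary:

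- For the annualized rate and continuous scores, use the difference in means from a linear model with arm, site, age group, gender and race/ethnicity as main effects, plus county within Community Place where recorded. This keeps the difference in means on which the sample size is based.
- For binary outcomes such as placement, use Cochran-Mantel-Haenszel stratified by site. If a rank test is used, make it van Elteren stratified by site.
- Use a variance estimate that allows for any household pairs enrolled before 22 February 2016.
- Take factor values from the participant logs where they correct the database, because the Protocol does not allow study arm, race, age, gender or site to be changed there after consent.
- Keep the unadjusted tests as a sensitivity analysis.

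The cost is SAP wording, eight adjustment terms at most (site 2, age 2, gender 1, race/ethnicity 2, county 1), merging the log corrections, and collapsing sparse categories. County is not among the variables that the Protocol lists for upload, so its availability should be confirmed first.

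### The one outcome that the trial is powered on is not named as the deciding test in the primary analyses, which cover several measures without multiplicity adjustment

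*SAP*

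**What the plan says.** **SAP, Sample Size Justification.** With 720 participants, power of 0.80/0.85/0.90 is stated for effect sizes of 0.209/0.223/0.242 "for the primary outcome measure of the annualized rate of hospitalization, ED use and institutionalization". The outcome is in the singular. The effect size is one mean difference divided by one common standard deviation.

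**SAP, Analysis Plan, paragraph on primary analyses.** Comparative effectiveness is to be judged by two-sample tests of the outcome measures. The error rule is: "These tests will be performed at a two-tailed significance level of 0.05 without adjustment for multiplicity". The paragraph then lists the measures: "Health care utilization and nursing home placement rates and self-rated health, wellness, depression, and anxiety between the two groups will be compared", and gives their level: "using a two-sample test again at a two-tailed significance level 0.05".

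**SAP, Analysis Plan, next paragraph.** It opens: "Subsequent to the primary analyses, regression analyses will be performed for the same outcome measures". The reference back places every listed measure inside the primary analyses. The same paragraph describes "intermediary measures of health and overall wellness such as self-rated health, depression, and anxiety in Aim 2" as possible mediators of the intervention's effect "on the primary outcomes measures in Aim 1". Here the primary outcomes are plural.

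**SAP, Analysis Plan, opening paragraph.** Three analyses are set out to serve both aims: (1) the pooled three-site comparison at 6 months, (2) AJFCS against the other two sites, and (3) 12 against 6 months of support within AJFCS. The text does not say which one decides.

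**The concern.** The sample size section and the analysis section do not describe the same primary test. The first has one combined rate. The second has utilization and placement rates, listed beside the Aim 2 measures, each at 0.05, and it never names the combined rate. Neither section gives a testing order or a rule for what counts as a positive trial.

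Declining to adjust for multiplicity is defensible when one endpoint has been designated to decide the question. Without that designation in the analysis section, the choice between the combined rate, the utilization rate and the placement rate could be made after the data are seen. Two things are then at stake: the error rate attached to a claim that peer support is effective, and whether the stated power belongs to the test on which that claim rests.

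**Working it through.** **1. Inputs.** From Sample Size Justification: N = 720, two-sided α = 0.05, effect sizes d = 0.209/0.223/0.242 in SD units. Assumption: 360 per group. The SAP states 1:1 only for AJFCS, but the protocol's recruitment goals are equal by arm at each site. From the Analysis Plan: α = 0.05 per test with no adjustment. Six measures are listed if each counts once, and two of them (utilization, placement) belong to Aim 1. The count would rise if hospitalization and ED use were tested separately.

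**2. The plan's own figure.** Power = Φ(d·√(n/2) − z), with n = 360, √180 = 13.416 and z = 1.960.
- d = 0.209: Φ(2.804 − 1.960) = 0.801
- d = 0.223: Φ(2.992 − 1.960) = 0.849
- d = 0.242: Φ(3.247 − 1.960) = 0.901

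The stated 0.80/0.85/0.90 is reproduced. It is the power of one test of one outcome at 0.05.

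**3. False positives when k tests could each decide.** Under no effect on any measure and independence, the chance of at least one is 1 − 0.95^k.
- k = 1: 0.05
- k = 2: 1 − 0.9025 = 0.0975
- k = 6: 1 − 0.7351 = 0.2649

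For correlated measures the documents give no correlations, so a range is assumed. Test statistics were simulated as Z_j = √ρ·C + √(1−ρ)·E_j, with standard normal C and E_j, 1,000,000 draws, rejecting when |Z_j| > 1.960.

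| Assumed ρ | 2 tests | 6 tests |
|---|---|---|
| 0.3 | 0.095 | 0.242 |
| 0.5 | 0.090 | 0.207 |
| 0.7 | 0.083 | 0.164 |
| 0.9 | 0.070 | 0.109 |

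Two decisive Aim 1 rates therefore give about 7–10%.

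**4. Ways to restore 5%.** The size needed for 80% power is total N = 4(z_{1−α/2} + 0.8416)²/d², rounded up per group, here at d = 0.209.

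| Approach | α per test | Power at 0.209/0.223/0.242, N = 720 | N for 80% at 0.209 |
|---|---|---|---|
| One designated primary test | 0.05 | 0.80/0.85/0.90 | 720 |
| Bonferroni, two Aim 1 rates | 0.025 | 0.713/0.774/0.843 | 872 |
| Bonferroni, six measures | 0.00833 | 0.566/0.638/0.729 | 1110 |

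Only the first leaves the sample size statement intact.

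**The case against.** A reader might infer that a positive trial can be claimed on any of the six measures, so that the error rate is 26%. The documents do not support that. No sentence authorizes a success claim on any single measure. The Analysis Plan calls the health and wellness measures intermediary, assigns them to Aim 2, and contrasts them with the Aim 1 primary outcomes. A claim resting on depression or anxiety alone would go against those labels. This stands, and it takes the Aim 2 measures out of the main figure. It does not settle how they are tested: the label appears only where mediation is described, and no sentence makes them secondary.

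A reader might also infer that a stated 5% error rate is wrong. It is not. The SAP states a level per test, discloses that it does not adjust, and claims no familywise control. No stated figure fails, and the power reproduces.

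Third, it can be said that the powered rate is tested after all. The outcome measures presumably include it, the t-test matches the effect-size definition, and utilization plus placement covers the same events. This is fair as far as it goes. Neither section defines how the rate is built, so the reading that there are two separate rates is an inference. But the reader then has to guess whether one test or several decide, and the singular and plural wording of the two sections supports different answers.

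Finally, the definitions of the two aims and the figures referred to are not in the text available, so a hierarchy could exist there. That limits the point to the text at hand. The mismatch between the two sections remains.

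**Conclusion.** The point holds in a limited form. The analysis section does not name the single powered outcome as the deciding test, places several measures in the primary analyses at an unadjusted 0.05, and disagrees with the sample size section on whether there is one primary outcome or more.

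The size depends on how the plan is read:
- If only the combined rate decides, the false-positive chance is 5% and nothing is lost.
- If the two Aim 1 rates each decide, it is about 7–10%. The 0.0975 assumes independence, and the lower values assume correlations up to 0.9.
- The 26% is an upper figure for six co-equal, independent measures and should not be quoted as the trial's error rate.

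All figures assume no true effect on any of the measures counted. The power figures assume 360 analysed per group; the SAP itself says that drop-out and death will reduce power. This is a cheap improvement to the plan, not a flaw in its sample size arithmetic.

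**What to change.** Three changes of wording in the SAP's Analysis Plan:

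1. State that the combined annualized rate from Sample Size Justification, in the pooled three-site comparison listed as analysis (1), is the single primary test, at two-sided 0.05.
2. Change the plural reference to the Aim 1 primary outcomes so that it agrees with Sample Size Justification.
3. Label the component rates and the Aim 2 measures as secondary, reported with estimates and confidence intervals as supportive evidence.

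The sample size and stated power are unchanged, and no new data are needed. The cost is that a significant result on a component rate or an Aim 2 measure can be presented only as supportive.

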The Effectiveness of Peer-to-Peer Community Support to Promote Aging in Place

Principal Investigator: [name]

Protocol Version Date: 10/30/2017

Coordinating Center: University of Wisconsin

Co-Investigators

[name]-University of Wisconsin
[name]- Alliance for Children and Families
[name]- Alpert Jewish Family and Children's Service
[name]- Community Place
[name]- Jewish Family Service of Los Angeles

Study Coordinator: [name]

Funding Sponsor: Patient Centered Outcomes Research Network (PCORI)

Statistical Considerations

In this section, we outline in detail the strengths of our proposed sampling and analysis plan and how it is designed to address and minimize the potential limitations of our study design. Specifically, we elaborate on how we plan to make our samples in the peer-support and standard community services group comparable, despite the fact we cannot randomize all participants; how we will control for differences across sites in our analyses; and how we will deal with missing data (including loss to follow-up).

Analysis Plan The mixed experimental and quasi-experimental, matched group comparison design allows us to conduct three different analyses to accomplish both Aims 1 and 2: (1) comparing the effectiveness of peer support to standard community services at 6 months combining data from all three sites; (2) analyzing the data from AJFCS and the combined data from the other two sites to assess the internal consistency of the effectiveness across the randomized and non-randomized designs but also to assess whether the effect size is different between the two components of the study design; (3) analyzing data from AJFCS to test whether peer-support is more effective when provided for 12 months compared to 6 months. For the third analysis using AJFCS data only, we will compare 12 vs. 6 month "dose"-levels of the peer-to-peer support intervention changes in the rates of health care utilization and nursing home placement and self-rated health, wellness, depression, and anxiety of between baseline and 12 months in group randomized to get peer support relative to changes in these same measures between 6 and 12 months in the group randomized to standard community services; as reminder this group received standard services for 6 months and then transitioned into receiving peer-support between 6 and 12 months (see Figure 3).

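### The 6-month comparison of the self-rated scales does not name the same scale's baseline score as a covariate, which costs precision at the site the SAP describes as randomised

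*SAP*

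**What the plan says.** The SAP's Analysis Plan sets a 6-month comparison of peer support with standard services across all three sites. For the Aim 2 scales it states that "self-rated health, wellness, depression, and anxiety between the two groups will be compared using a two-sample test". It does not say whether the scores themselves or changes in them are tested.

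Regressions come after the primary tests, "adjusting for stratification factors and other potential confounders that might influence the outcomes, including an indicator for site". The stratification factors, in the SAP section on randomization and matching, are age, gender and race/ethnicity. The other confounders are not listed, and no scale's baseline score is named.

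Analysis (3), which uses AJFCS data only and compares 12 with 6 months of support, works with changes in "self-rated health, wellness, depression, and anxiety of between baseline and 12 months" for the peer-support group. The plan therefore expects a baseline score to exist. The protocol, under Consent and Baseline Visit, describes one baseline survey at consent and does not distinguish by group. The survey items are in a separate document.

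On design, the SAP allocates AJFCS participants "in a 1:1 ratio using permuted block randomization, stratified by age, gender and race/ethnicity". At the other two sites it matches existing recipients to people on the waiting list, on the same three demographic factors. The protocol reads differently. Its AJFCS recruitment section draws the peer-support group from current recipients and the controls from the community, and its Matching section has wait-list people matched to existing recipients at all sites.

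**The concern.** A person's earlier score on a scale usually predicts the later score better than age, gender, race/ethnicity or site does. Leaving it out of the 6-month comparison puts predictable between-person variation into the error term. The Aim 2 confidence intervals are then wider than the data require.

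The open-ended reference to other confounders does not settle this. A covariate left unnamed can be added or dropped after the data are seen, and here it would enter only in an analysis that follows the primary test. What is at stake is how small an effect on self-rated health, wellness, depression or anxiety the randomised part of the study can detect.

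**Working it through.** **The plan's own figure.** The SAP states that "Given the total sample size of 720 at-risk older adults" the study has "0.80/0.85/0.90 power to detect the effect size of 0.209/0.223/0.242". The significance level is two-sided 0.05 without multiplicity adjustment. The effect is a mean difference "divided by the standard deviation of the annualized rate assumed to be common in the two groups", so SD = 1. Taking 720 as 360 per group, the detectable effect is (1.960 + z) × √(2/360), with √(2/360) = 0.0745:

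- 80% power: 2.802 × 0.0745 = 0.209
- 85% power: 2.996 × 0.0745 = 0.223
- 90% power: 3.242 × 0.0745 = 0.242

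All three figures reproduce. They concern the annualized utilization rate; the SAP gives no power for the Aim 2 scales. The same formula is used below only to put the gain on a familiar scale.

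**AJFCS without adjustment.** The protocol's recruitment goal for AJFCS is 300, or 150 per group. The detectable effect at 80% power is 2.802 × √(2/150) = 2.802 × 0.1155 = 0.32 SD.

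**AJFCS with the baseline score in the model.** If r is the correlation between the baseline and 6-month scores, residual variance is multiplied by 1 − r² and the standard error by √(1 − r²). The equivalent gain in sample size is 1/(1 − r²). The documents do not give r. The range taken is 0.4 to 0.7, with 0.3 added as a pessimistic case.

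| r (assumed) | Residual variance | Standard error | Sample-size equivalent | Detectable effect, 150 per group |
|---|---|---|---|---|
| 0.3 | 0.91 | 0.954 | 1.10 | 0.31 SD |
| 0.4 | 0.84 | 0.917 | 1.19 | 0.30 SD |
| 0.5 | 0.75 | 0.866 | 1.33 | 0.28 SD |
| 0.7 | 0.51 | 0.714 | 1.96 | 0.23 SD |

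Across 0.4 to 0.7 the variance falls by 16% to 51% and the standard error by 8% to 29%.

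**If the test is meant to be on changes.** With equal variances at the two times, a change score has variance 2(1 − r): 1.2 at r = 0.4 and 0.6 at r = 0.7. The ratio of adjusted to change-score variance is (1 − r²)/[2(1 − r)] = (1 + r)/2, or 0.70 and 0.85. Covariate adjustment then still removes 30% and 15% of the variance respectively. Below r = 0.5 the change score is noisier than the unadjusted 6-month score.

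**The case against.** Several objections have force.

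*The plan does use baseline.* Analysis (3) is built on change from baseline, so it would be wrong to say that no planned analysis uses it. But it addresses duration of support at one site, not the 6-month comparison between groups.

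*The text leaves room for baseline.* The two-sample test might be on changes, and the unnamed confounders might include the baseline score. Both are possible, so the accurate statement is that the covariate is not named, not that it is excluded. As shown above, a test on changes would still be less efficient than adjustment.

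*The gain is measured against the unadjusted test.* This stands. Against a regression already containing demographics and site, the gain would be somewhat smaller. How much smaller cannot be computed from the documents.

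*The scales may not all be continuous.* Their formats are not given, so a linear model cannot be prescribed for every one.

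A reader might also infer that omitting baseline biases the 6-month result. At r = 0.4 to 0.7, a baseline gap of 0.2 SD would carry 0.2 × r = 0.08 to 0.14 SD into the later difference. The documents do not support calling that bias throughout. Under randomisation a gap arises by chance, and the unadjusted test remains valid. At Community Place and LA the recipients are already supported when baseline is measured, so a gap may be part of the benefit, and removing it is not clearly removing an error.

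For the same reason, a reader might want one baseline-adjusted model over all sites. The site goals sum to 226 + 300 + 60 = 586, or 293 per group, and pooling would lower the detectable effect from 0.23 SD to 0.21–0.17 SD. If AJFCS is randomised, however, that coefficient would average starting support at AJFCS with continuing support elsewhere and answer neither question.

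**Conclusion.** The point holds as one of efficiency at AJFCS. The 6-month comparison of the self-rated scales does not name the own-baseline score, and naming it would lower the detectable effect there from about 0.32 SD to about 0.30–0.23 SD. It does not show that the planned test is invalid.

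The size rests on five assumptions:

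- r lies between 0.4 and 0.7; at 0.3 the variance gain is only 9%.
- The comparator is the unadjusted test of 6-month scores.
- The AJFCS goal of 150 per group is met. No drop-out is applied; losses raise the adjusted and unadjusted figures in the same proportion.
- The scales are measured at baseline in both groups. This is inferred from analysis (3), which uses baseline scores explicitly only for the peer-support group, together with the common baseline survey.
- AJFCS is randomised, with baseline taken before support begins. The protocol's recruitment and matching sections put this in doubt. If existing recipients were enrolled there too, the adjusted estimate at AJFCS is also one of continuing support.

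**What to change.** 1. Reconcile the SAP's statement that AJFCS is randomised with the protocol's AJFCS recruitment and Matching sections, and state whether baseline there precedes support.
2. For AJFCS, pre-specify the 6-month comparison of each scale as a model of the 6-month score on group, the same scale's baseline score and the stratification factors. Use a linear model for continuous scales and the corresponding generalised linear model otherwise. Keep the two-sample test as supporting, and say whether it is on scores or changes.
3. For Community Place and LA, report the baseline-adjusted estimate separately, labelled as the effect of continuing support, beside the unadjusted comparison. Do not combine it with AJFCS in one coefficient. Analysis (2) already separates AJFCS from the other two sites, so no new structure is needed.
4. If AJFCS also enrolled existing recipients, apply the continuing-support label there as well.

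The change needs SAP wording and standard models and, provided the baseline survey holds these scales as analysis (3) implies, no new data. The price is slightly more analysis and a narrower stated estimand at the non-randomised sites.
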